**Section 3 Regulatory Criterion for Approval: Equitable Selection**

**Selection of subjects is equitable. In making this assessment the IRB should take into account the purposes of the research and the setting in which the research will be conducted. The IRB should be particularly cognizant of the special problems of research that involves a category of subjects who are vulnerable to coercion or undue influence, such as children, prisoners, individuals with impaired decision-making capacity, or economically or educationally disadvantaged persons.**

- No population is unfairly targeted
- No population is unfairly excluded
- Burdens are distributed fairly
- Benefits are distributed fairly

## Protocol Summary/Submission Application

The research population includes the following:	Check all that apply:
Normal adults/health volunteers	
Inpatient population	
Outpatient population	
CW or MCW Employees/Staff	
Students of (describe) Click here to enter text.	
Residents/Fellows	
Prisoners	
Children	
Pregnant Women, Fetuses, Neonates (of uncertain viability or nonviable), after delivery, placenta, dead fetus, or fetal material	
Adults with Impaired Decision-Making Capacity (enrolled by legally authorized representative)	
Individuals with limited English proficiency ( specify anticipated primary language ): Click here to enter text.	
Economically disadvantaged persons	
Educationally disadvantaged persons	
Other ( describe ): Click here to enter text.	
A. Total number of human research subjects proposed:	

Locally: 20 parent/child dyads who complete the study / Study-wide (if applicable): N/A
 
Describe what are these numbers are based on: There are 380-400 PICU admissions/year that are seen by ICU Neurology. Using a conservative estimate of 8-10% incidence of PSH, we expect to have 35-40 patients with PSH. At a conservative 60% enrollment rate, we expect to be able to successfully enroll 20 patients in this pilot study who complete the study and 20parents/legal guardians to take the parental questionnaire.
	
B. How do you plan to identify subjects for recruitment or records for inclusion in the study?	

All of the eligible patients (those with acute severe brain injury) would already have had an ICU Neurology consult. If they exhibit symptoms of PSH per Neurology and Critical Care teams routine assessment, a member of treatment team will evaluate their interest to hear about a research study. If they agree to hear about a research study, one of research team members will approach the family for consent..
 
For the historical controls, the Neurology ICU Billing administrative dataset will be used to collect the MRNs of patients who meet the broad criteria of TBI.
	
C. Eligibility Criteria (inclusion/exclusion criteria):	
Inclusion criteria:	

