### **Aim 3b: Evaluate feasibility of measuring PENFS effectiveness in treating PSH by a decrease in medication use**

**Methods:** The maintenance medications and the number of doses and type of rescue medications administered will be collected for every 24 hours (0-24h, 25-48h, 49-72h, 73-96h, 97-120h, 121-144h, 145-168h, 169- 192h) for the enrolled patients. These will be compared to a historical cohort of PSH patients. The historical cohort will consist of PSH patients (2-17 years old) identified using the ICU Neurology administrative dataset from January 2018 – August 2021. This dataset will be used to identify ASBI patients who likely developed PSH. Eligible patients with PSH will be identified and relevant data collected by individual chart review. During this period all the PSH patients were followed by ICU Neurology thus ensuring a uniform approach to their treatment. We have also developed a practice guideline for treatment of PSH that will ensure uniform treatment of these patients during the study period. Similar to Aim 2a, we will examine the need for additional maintenance medications or change in frequency of rescue medications with discontinuation of the device. We hypothesize that, with discontinuation of the device, the patients may experience worse PSH symptoms as demonstrated by increasing CFS score and need for additional maintenance and/or rescue medications.

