## Protocol Summary/Submission Application

complete the study. If the patient does meet CFS scoring criteria for study enrollment, we will collect the CFS score for a 12-hour period before placement of the device followed by every 12 hours while the device is in place and for an additional 72 hours after removal of the device.

**Data collection & Management:** We will collect demographics, cause of ASBI, imaging findings, sedative, pain and other neurotropic medications, and maintenance and rescue medications for PSH including their number and doses for every 24-hour period from placement of the device. We will also collect all the HRV and pupillometry parameters for the 12-hour period before and after placement of the device. For the historical cohort, we will collect demographics, cause of ASBI, imaging findings, maintenance and rescue medications used in each 24 hour period for the first 120 hours and then additional 72 hours from the time of meeting CFS score > 6 criteria. . The REDCap database for this study will be developed and managed by Quantitative Health Sciences on MCW-secure servers

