## Protocol Summary/Submission Application

*Hypothesis 1:* The number approached and consented will be tracked. Reactions/ adverse events will be summarized and reasons for early termination, if any, evaluated.

*Hypothesis 2a, 2b:* The scoring tool will be adapted for the appropriate age range of the patient (Table 2). We aim for at least 80% scoring ( $\geq 8/10$  scheduled scoring per protocol while the device is worn). The association of the score and the number of doses of maintenance and rescue medications will be summarized with a spearman correlation and exact 95% Confidence intervals (CI).

*Hypothesis 3a:* HRV and Pupillometry measures will be tracked over time with any loss of data recorded with reasons. Wilcoxon Rank Sum test will be used to compare the mean  $\pm$ SD for the parameters for the 12-hour periods before and after device placement.

*Hypothesis 3b:* The number of doses of maintenance and rescue medications for control of PSH symptoms will be compared to historic data using a t-test or non-parametric Mann Whitney. Further a classification tree will be used to evaluate the effect of demographics, clinical history and use of PENFS.

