## Protocol Summary/Submission Application

- 1) Children admitted to the PICU aged 2-17 years
- 2) Acute severe brain injury (ASBI) and symptoms of PSH- defined as CFS score > 6 (moderate severity of PSH)

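### The protocol names two source populations for the Aim 3b historical controls (ASBI in the methods, TBI in the record search); if the TBI wording is followed, cause of injury cannot be separated from the device among non-TBI patients

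*Combined protocol and SAP*

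**What the plan says.** Two places describe how the historical cohort is found.

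- Section 1, item E, Aim 3b methods, on the ICU Neurology administrative dataset: "This dataset will be used to identify ASBI patients who likely developed PSH". A second step follows: "Eligible patients with PSH will be identified and relevant data collected by individual chart review".
- Section 3, item B, which answers how records will be located: the Neurology ICU billing dataset "will be used to collect the MRNs of patients who meet the broad criteria of TBI". The paragraph just before it describes the prospective patients as having acute severe brain injury.

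The device group is defined in Section 3, item C: "Acute severe brain injury (ASBI) and symptoms of PSH- defined as CFS score" above 6. No cause of injury is specified.

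Cause is recorded in both groups under Data collection & Management. For PENFS patients: "We will collect demographics, cause of ASBI, imaging findings, sedative, pain and other neurotropic medications". For controls: "For the historical cohort, we will collect demographics, cause of ASBI, imaging findings, maintenance and rescue medications used in each 24 hour period".

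The Hypothesis 3b analysis states that dose numbers "will be compared to historic data using a t-test or non-parametric Mann Whitney". It then adds: "Further a classification tree will be used to evaluate the effect of demographics, clinical history and use of PENFS". No matching, restriction or stratification by cause of injury is described.

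**The concern.** ASBI and TBI are not the same population in this protocol. The Background treats severe traumatic injury and anoxic injury as separate causes with different PSH incidence. Two people building the control cohort, one from the Aim 3b methods and one from Section 3, item B, could therefore end up with different patients.

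The comparison has a stated use. Aim 3b says that it is to support power and sample-size work for a later efficacy trial, while acknowledging that this pilot is not powered for efficacy. The lack of power concerns precision. It does not protect the comparison from a systematic difference between the cohorts. If drug use differs by cause of injury, a control group confined to TBI would mix that difference with whatever the device does.

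**Working it through.** The plan gives no control-cohort size, effect size or SD for Aim 3b, so there is no figure to reproduce. The check compares the sections and follows each reading through to the analysis.

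**1. Are the two populations different?** The Background gives PSH incidence of 10–20% among survivors of severe TBI and about 30% among survivors of anoxic injury. Per survivor, PSH is thus 0.30/0.20 = 1.5 to 0.30/0.10 = 3 times as frequent after anoxic injury. Non-TBI patients are therefore a real possibility in an any-cause device group. These are incidences within cause. They do not give the cause mix of PSH patients in this unit, and the same paragraph says that PSH is most often seen with severe TBI.

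**2. Can later steps repair a TBI pull?** The order is dataset first, chart review second. Chart review removes records from the list that was pulled. It cannot add a patient whose record number was never collected.

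**3. What would the analysis then contain?** If the pull is confined to TBI:

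| | PENFS | Historical |
|---|---|---|
| TBI | some of the 20 | all controls |
| Non-TBI | the rest of the 20 | none |

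The lower right cell is empty. The t-test or Mann-Whitney test uses no covariates and compares whole columns. The tree may split on clinical history, but in the non-TBI row every patient has the device, so it has no contrast to estimate there.

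**4. How large is the effect?** Let q1 and q0 be the non-TBI shares of the PENFS and historical groups, and d the difference in mean dose count, non-TBI minus TBI, without the device. For a difference in means, the expected shift due to cause is (q1 − q0) × d. With TBI-only controls q0 = 0, so the shift is q1 × d. The documents give neither q1 nor d, nor the sign of d, so no number can be put in. The formula does not describe a Mann-Whitney result.

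**5. The other reading.** If controls come from ASBI and have the same cause mix as the PENFS group, q1 = q0 and the expected shift is 0. An equal mix is an assumption. Drawing from ASBI makes it possible but does not guarantee it.

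**The case against.** The best defence is that ASBI is plainly intended. The Aim 3b methods are the scientific text, and a field for cause of ASBI in the historical cohort would have little purpose if every control had TBI. Against this stands one sentence in an application-form item, and it refers to broad criteria without saying that only TBI will be used. This is a fair argument about intent. It does not remove the problem, because item B is the place that says how records are found.

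A reader might infer that the investigators chose TBI-only controls by design. The text does not support that; it supports an unresolved inconsistency. A reader might also infer that the device effect will be overstated, or by how much. No section says that drug use differs by cause, so neither claim can be made.

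The plan also has partial safeguards. Its exploratory analysis covers distributions and relationships of the variables and could include a table of cause by cohort, although none is named. The tree can use clinical history, which helps if controls include non-TBI patients. Some chance imbalance in cause would arise with any small historical cohort and is not a fault of this plan.

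Finally, handling cause does not make the cohorts comparable in other respects. For example, new maintenance drugs are barred for 12 hours after device placement, and no such restriction is described for the controls. That objection stands and limits what a stratified result can claim.

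**Conclusion.** The contradiction is real and should be resolved. Confounding of cause with device is conditional: it follows only if the pull is made as Section 3, item B is worded and TBI there is read as excluding other causes. Under that reading, non-TBI PENFS patients have no counterparts among the controls, and no analysis in the plan can supply them. A bias then arises if at least one of the 20 PENFS patients has a non-TBI cause and drug use differs by cause. Its size and direction cannot be derived from the documents. If the Aim 3b methods are followed, the contradiction has no consequence for the cohort, and a clear display of cause by group is all that remains useful.

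**What to change.** 1. Before record numbers are pulled, amend Section 3, item B so that controls come from the same ASBI population as the Aim 3b methods and the inclusion criteria. If the pull has already been made, state the definition that was used.
2. If TBI-only controls are intended, say so and restrict the Aim 3b comparison to TBI patients in both cohorts.
3. Tabulate cause of ASBI by cohort.
4. Beside the planned test, report the PENFS-minus-historical difference in dose counts with a CI, stratified by TBI v non-TBI. Label it a descriptive sensitivity result and note that other differences between the cohorts remain. Under option 2 this stratification is not needed.

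The cost is a wording change, one table and a sentence or two of analysis text; cause is already collected in both cohorts. Searching for ASBI needs an operational definition for the record search and may add chart review. The TBI-only option leaves fewer than 20 PENFS patients in the comparison if any have another cause. With 20 PENFS patients at most, stratum-level intervals will be wide.

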## Protocol Summary/Submission Application

- 1) Children admitted to the PICU aged 2-17 years
- 2) Acute severe brain injury (ASBI) and symptoms of PSH- defined as CFS score > 6 (moderate severity of PSH)

**Exclusion criteria:**

- 1) age < 2 years (small ears thus less surface area to apply the leads)
- 2) ear deformity
- 3) severe dermatitis of ear lobes
- 4) intractable seizures
- 5) heart block
- 6) other implantable devices (cardiac pacemaker, vagal nerve stimulator, etc.)
- 7) known pregnancy
- 8) Parent or LAR under the age of 18.

**D. Who will be responsible for determining whether potential subjects satisfy eligibility criteria and how will they do so?**

**Note:** if the analysis of health information is necessary to determine eligibility, a medically-qualified person must be involved in the determination.

Eligibility will be determined by either the Principal Investigator or Sub-Investigator. A checklist of the Inclusion/Exclusion criteria will be followed to determine eligibility.

**E. Will recruitment materials be used?**

No  Yes

If YES, describe how and where materials will be posted/distributed: [Click here to enter text.](#)

Documents containing exact language to be used must be included in submission package for review and approval by the IRB. Review [Guidance – Recruitment for Human Subject Research](#) (found in IRBNet under Forms and Templates) for more information and instructions for logo use.

### Section 4 Regulatory Criterion for Approval: Informed Consent Process

**Informed consent will be sought from each prospective subject or the subject's legally authorized representative, in accordance with, and to the extent required by, §46.116./50.20.**

- Circumstances of the consent process will provide the subject sufficient opportunity to consider whether to participate (this is an ongoing process and should be confirmed at the time of each interaction)
- Circumstances of the consent process will minimize the possibility of coercion or undue influence
- Information will be given in an understandable language
- Special issues that could present undue influence and need additional consideration: advertisements, payment for participation

### Description of Process to Obtain Consent

**Information regarding parental permission and assent is captured in Section 8: Vulnerable Populations.**

## Protocol Summary/Submission Application

**A. WHO: List appropriately trained personnel *by role* rather than individual name (i.e., Investigators, Study Coordinators, etc.) who have been delegated authority by the PI to conduct the consent process, and indicate whether those individuals have an existing treating relationship with the potential subject:**

Members of study team including research coordinators will conduct the consent process. None of these will have an existing relationship with the potential subject.

**B. WHEN: Describe when subjects are being informed of the research opportunity and how much time they are given to consider whether to participate:**

The local research team will screen all admitted PICU patients to determine the eligibility for study. Once eligibility is confirmed, the study team will reach out to attending physician and clinical team to obtain their permission to approach the subject and family. If the clinical team is ok for the subject to participate in the study, someone who has a treating relationship with the subject will make the initial contact, introducing the research study and study team to the subject and their family. It is expected that ample time will be provided to subject's family so they can think about participation and receive answers to any questions they may have.

Parent as Participant: After the main study consent is signed, parent(s)/guardians will be given the "CHW Minimal Risk template" to read and discuss. All of their questions regarding this consent, which pertains to completing a brief questionnaire about their perceptions of their child's involvement in this device study will be answered. It is expected this consent process will take approximately 15 minutes.

After the consents are signed, the CFS assessment will be made to ascertain study eligibility. If the child does not meet eligibility criteria based on their CFS scores, the family will be told their child is not eligible for the study as they did not meet study defined CFS scoring criteria. Study Enrollment is defined as meeting CFS criteria of > 6 after consent. If CFS scores are already being collected for subject prior to subject consent as a standard of care, we can use already available CFS scores from medical record. The PENFS device will be placed over the external ear by study investigator or one of trained nurses (RNs) from the Pediatric Translational Research Unit (P-TRU) within 24 hours of meeting CFS > 6 score criteria

**C. WHERE and HOW: Describe the physical location of the consent discussion and how it will be conducted:**

Someone who has a treating relationship with the potential subject will make initial contact with the patient, obtain permission for the study team to approach, study team will then approach the patient and family for consent discussion in private setting in PICU.

**D. SPECIAL CONSIDERATIONS: Describe any subject compensation (reimbursement for expenses; compensation for time and effort):**

No subject compensation is offered in this study.

**E. If you are requesting to waive consent for some or all subjects, provide rationale:**

We are requesting a full waiver of assent for this study as we do not anticipate any of the subjects will be able to assent because of their severe brain injury. These patients will either have reduced consciousness or will cognitively not be able to understand what they are consenting/assenting to.

Include **IRB – Request form for Alteration or Waiver of Assent, Consent, Parental Permission** (found in IRBNet under Forms and Templates) in the submission package.

## Protocol Summary/Submission Application

### Section 5 Regulatory Criterion for Approval: Documentation of Informed Consent

**Informed consent will be appropriately documented or appropriately waived in accordance with §46.117/50.27.**

**A. Describe the plan for documentation of consent and process that is specific to the protocol and consistent with local requirements:**

If you are requesting to waive documentation of consent/assent/parental permission, include **IRB – Request form for Alteration or Waiver of Assent, Consent, Parental Permission** (found in IRBNet under Forms and Templates) in the submission package.

The study team anticipates an adequate number of qualifying patients to be available within the PICU. These patients will be identified during their PICU stay and approached if they meet the study inclusion criteria and do not meet any of the exclusion criteria. The research coordinator or other members of research team will approach the family for consent after receiving permission from the clinical team. If the principal investigator is part of the potential subject's care team he/she will not approach the family and one of the sub-investigators or research coordinators will participate in the consent conversation instead. Someone who has a treating relationship with the potential subjects will make the initial contact with the patient, obtaining permission for the study team to approach, and a member of study team will then approach the patient and family for research study participation. The research team will meet with the patient and their parent(s)/ legal guardian to discuss the study and obtain consent. A copy of the consent signed by the parent(s)/ legal guardian will be uploaded into the patient's medical record. A signed copy of the consent will be given to the patient's parent(s) or legal guardian.

Parent as Participant: The original consent and documentation will not be scanned into the child's medical record, but will be secured in the subject's study file in a locked cabinet along with other study documents. The parent(s)/guardian will be given a signed copy of the Minimal Risk template.

### Section 6 Regulatory Criterion for Approval: Safety Monitoring

**When appropriate, the research plan makes adequate provision for monitoring the data collected to ensure the safety of subjects.**

Considerations applicable to research that is deemed greater than minimal risk include:

- Who reviews safety data?
- What data are reviewed (safety and efficacy)?
- When/how often are data reviewed?

**A. Is a Data Safety Monitoring Board (DSMB)/Data Monitoring Committee (DMC) in Place?**

**No**    **Yes**    **N/A (study is not greater than minimal risk)**

If **YES**, describe its members and how often they meet (you may include any DSMB/DMC charters in the submission package; once the study has been opened locally any DSMB/DMC reports should be submitted for review as reportable new information):

## Protocol Summary/Submission Application

**B. If there is no formal DSMB/DMC, describe the monitoring plan or indicate that the study involves no more than minimal risk (if the IRB disagrees and determines the study to be greater than minimal risk, the study will be deferred until an appropriate monitoring plan has been developed):**

Members from the division of critical care (MD, APP) will meet every 2 months to review data on device safety. Any serious adverse event deemed related to study will be notified immediately for adjudication.

**C. Have stopping rules been established for the study (to evaluate whether the objectives have been met, or that the objectives cannot be met, or that the accumulated data indicates that the risks exceed the benefits of the study)?**

No  Yes  N/A (study is not greater than minimal risk)

If YES, describe the stopping rules:

Any symptomatic cardiac dysrhythmia or new-onset seizure deemed to be as a result of the device use.  
 5 consecutive patients showing device intolerance i.e worse comfort scores, worse CFS score,

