### **E. Design and methods (including experimental design, technical details and laboratory methodology):**

#### **Design & Methods**

In this prospective unblinded pilot study we will enroll eligible patients until 20 parent/child dyads complete the study. It is expected many of the consented patients will not meet the eligibility criteria of CFS score > 6 (moderate severity of PSH). Those children will be considered Screen Failures and their parents/LAR told they are ineligible to continue in the study. Children admitted to the PICU at CW aged 2-17 years with ASBI and symptoms of PSH with a CFS score > 6 (moderate severity of PSH) will be eligible for inclusion. Exclusion criteria include age < 2 years (small ears thus less surface area to apply the leads), ear deformity or severe dermatitis of ear lobes, intractable seizures, heart block, patients with other implantable devices (cardiac pacemaker, vagal nerve stimulator, etc.) or known pregnancy.

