### **Aim 1: Identify and enroll 20 pediatric patients with ASBI and PSH.**

**Methods:** Parent(s)/legal guardians, 18 years or older, will be approached for informed consent if their child has ASBI and is exhibiting clinical signs and symptoms of PSH. Once consented, the CFS scoring tool (Table 1a,) will be used to evaluate patients felt to be exhibiting symptoms of PSH to identify eligible ASBI patients. Patients with CFS score > 6 will be eligible for enrollment in the study.

Families of patients who do not meet the CFS score criteria > 6 will be told their child did not meet scoring criteria of study and will be considered consented but not enrolled in study.

Study Enrollment is defined as meeting CFS criteria of > 6 after consent. If CFS scores are already being collected for subject prior to subject consent as a standard of care, we can use already available CFS scores from medical record. The PENFS device will be placed over the external ear by study investigator or one of trained nurses (RNs) from the Pediatric Translational Research Unit (P-TRU) within 24 hours of meeting CFS > 6 score criteria..

There are 380-400 PICU admissions/year that are seen by ICU Neurology. Using a conservative estimate of 8-10% incidence of PSH, we expect to have 35-40 patients with PSH. At a conservative 60% enrollment rate, we expect to be able to successfully enroll 20 patients in this pilot study. Previous studies using the device has shown it to be well-tolerated with minimal side effects (25,26). In a large, randomized sham-controlled trial Kovacic et al showed a very low rate of discontinuation of the device due to side effects. We hypothesize that the dropout rate will be ≤ 10%. Tolerability of the device will be assessed by subjective assessments of device tolerance by the bedside nurse, the CFS score (increasing score after device placement would suggest worsening PSH symptoms) and skin integrity (bedside nurses will perform routine skin evaluation and care while the device is in place.). To evaluate safety, we will monitor for serious adverse effects such as cardiac dysrhythmia (EKG monitoring), and new-onset seizures.

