**B. Describe steps taken to minimize risks:**

Patient comfort will be monitored to assess tolerability, skin will be monitored for contact dermatitis. EKG/Heart rate monitoring for dysrhythmia and monitoring for new onset clinical seizures. To minimize the remote possibility of a breach in confidentiality, patient data including PHI will be assigned a study ID and stored in a password-protected Excel file on MCW's secured drive: and be only accessible to limited members of the study team. Only coded data with a Study ID will be entered into the password-protected REDCap database.

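### The seizure stopping rule covers only new-onset seizures, so a device-related recurrence in an eligible child with earlier controlled seizures would not trigger the study stop

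*Combined protocol and SAP*

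**What the plan says.** Section 6, item C lists two stopping rules. The first is "Any symptomatic cardiac dysrhythmia or new-onset seizure deemed to be as a result of the device use". The second is five consecutive patients with device intolerance, described by comfort and CFS scores.

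Seizure monitoring is named in two places. The Aim 1 methods say "To evaluate safety, we will monitor for serious adverse effects such as cardiac dysrhythmia (EKG monitoring), and new-onset seizures". The risk-minimisation item (Risks, item B) says "EKG/Heart rate monitoring for dysrhythmia and monitoring for new onset clinical seizures". Risks, item A also lists new-onset seizures, with cardiac dysrhythmia, as the theoretical device risks.

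On eligibility, Design & Methods excludes children with "ear deformity or severe dermatitis of ear lobes, intractable seizures, heart block", among other conditions, and the exclusion list in Section 3, item C repeats "intractable seizures". The inclusion criteria set no condition on seizure history.

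The general safety provisions are wider. Table 3 schedules adverse-event collection through 192 hours. The analysis text for Hypothesis 1 says "adverse events will be summarized and reasons for early termination, if any, evaluated". Section 6, item B has critical care staff review device safety every 2 months and adds "Any serious adverse event deemed related to study will be notified immediately for adjudication".

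**The concern.** The population that may enrol and the event that stops the study do not match. A child with acute severe brain injury who has had seizures that are now controlled is eligible. If the device brings on another seizure in that child, or makes the seizures worse, the event is not new-onset in the usual clinical sense of a first seizure.

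Seizure is one of only two theoretical serious risks that the protocol attributes to the device. A rule that stops the study for a device-caused seizure should not depend on whether the affected child happened to have had one before. What is at stake is whether later enrolment halts automatically after such an event or continues unless the people adjudicating it decide otherwise.

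**Working it through.** No arithmetic applies. The plan attaches no figure to this rule, so the check is a comparison of every statement about seizures.

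1. **Who can enrol.** Both places that list exclusions (Design & Methods; Section 3, item C) name intractable seizures only. Neither mentions earlier, controlled or early post-injury seizures. Such children are therefore eligible if they meet the other criteria.

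2. **What is named for monitoring.** Both statements (Aim 1 methods; Risks, item B) are limited to new-onset seizures. The Aim 1 list is introduced as a set of examples, so it is open. The Risks statement is not phrased that way.

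3. **What stops the study.** The seizure limb has two conditions joined together: the seizure is new-onset, and it is judged to result from the device. The intolerance limb does not fill the gap, because it needs five patients in a row and refers to comfort and CFS scores, not seizures.

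4. **What else catches the event.** Adverse-event collection, the Hypothesis 1 summary, the two-monthly review and immediate adjudication of related serious events all apply whatever the seizure history. None of them is stated to stop the study.

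5. **The same event in two children.** Suppose a seizure occurs on the device and is judged to be caused by it.

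| | No earlier seizure | Earlier controlled seizures |
|---|---|---|
| Eligible | Yes | Yes |
| Can be recorded and summarised as an adverse event | Yes | Yes |
| Adjudicated at once if serious | Yes | Yes |
| Meets the seizure stopping rule as ordinarily read | Yes | No |

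Only the last row differs, and only because of the word new-onset.

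6. **What that word adds.** Seizures from the underlying injury are already screened out by the requirement that the device be judged the cause. The new-onset condition has a separate effect only after that judgement has gone against the device. At that point it removes children with a seizure history from the rule.

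**The case against.** There are five arguments on the other side.

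**The term is undefined and could be read more widely.** New-onset might mean any seizure that starts after placement, and on that reading there is no gap. The reading is possible, but the text does not state it and it is not the usual meaning. It would also make the word redundant, since a seizure caused by the device must follow its placement. If the wider meaning was intended, the proposed wording simply says so.

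**The event is already handled.** This stands in large part. A reader might infer that a recurrent seizure would go unmonitored or unrecorded. The documents do not support that: the adverse-event provisions are general and related serious events go straight to adjudication. Nothing prevents those adjudicating from stopping the study, and the existing trigger also waits on a judgement of relatedness. What remains is the difference between a stop that the rule requires and one that is left to discretion.

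**The rule protects the study, not the child.** This also stands. A reader might infer that children with a seizure history are individually less well protected. The stopping rules do not decide whether the device comes off a particular child. Patients with this injury are co-managed by ICU Neurology and monitored as inpatients while the device is on. Any gap bears on later enrollees in general, whatever their own history.

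**Seizure history should be a named baseline item.** A reader might add this as a second fault, because the data collection plan names no such item. The documents do not make it one. The plan's lists are not shown to be exhaustive, Section 3, item D says "A checklist of the Inclusion/Exclusion criteria will be followed to determine eligibility", and the chart is available. Once any device-related seizure triggers the rule, stopping no longer depends on classing a seizure as new or recurrent.

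**Adjudication may be the better route for recurrences.** In a brain-injured child with earlier seizures it is harder to attribute a recurrence to the device, and a mandatory halt after one event could be thought too strict. That would be a defensible choice, but the protocol does not state it. The difficulty is also already met by the relatedness clause.

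**Conclusion.** The point holds as a minor one with a cheap improvement. As ordinarily read, the seizure limb does not stop the study for a recurrent or worsened seizure that has been judged device-caused in a child with earlier controlled seizures, although that child is eligible and the same event in another child would stop it. The two monitoring statements carry the same limit.

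The conclusion rests on one assumption, that new-onset means a first seizure in a child with none before. It does not rest on any prevalence or event rate. The documents give neither the share of the 20 planned children who will have had earlier seizures nor a rate of seizures caused by the device, and they report no new-onset seizure in previous studies of it. Figures for how many children might fall outside the rule would be guesses and would not measure harm. The finding is confined to the automatic stop and the named monitoring. It does not extend to a failure of safety capture or to the care of the individual child.

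**What to change.** In Section 6, item C, reword the seizure limb so that it covers any seizure after device placement, whether new, recurrent or worsened, and keep the existing requirement that it be judged to result from the device. In the Aim 1 methods and in Risks, item B, drop the new-onset limit so that the monitoring statements refer to seizures in general.

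The cost is an IRB amendment changing three statements. A few more events will need a relatedness judgement, some of them due to the underlying illness, and a recurrence judged related would now stop the study. Eligibility, sample size and procedures do not change, and no extra baseline item or set of seizure definitions is needed. If the sponsor would rather send recurrences to adjudication than have them stop the study, the protocol should say so in Section 6 and give the reason.
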